Date:	5-9-19
Title	Does procedural timing impact perioperative morbidity in elective surgery?
Principal Investigator:	[name] MD
Sub-Investigators:	---
Research Specialist	[name] , [name]
TriHealth Department Affiliation:	Urogynecology Division of Ob/Gyn
Hatton #:	16-049

**IRB Review Type:**  Exempt  Expedited  Full Board

**Purpose of Study:** Please describe:

To evaluate if there are differences in perioperative morbidity for elective surgery based on the time of the year surgery is performed.

#### **Hypothesis or Research Question**

We hypothesize that surgical complication rates are higher at certain times during the year than others. Specifically;

Primary hypothesis: Perioperative morbidity will be highest toward the end of the calendar year (December) corresponding with insurance deductible year-end.

Secondary hypothesis: Perioperative morbidity will be high as well with the start of academic trainees (July).

#### **Background**

Surgical complications are a significant cause of morbidity and mortality. Surgical complications account for up to 40% of hospital complications [1]. Complications and adverse events are also becoming increasingly important for measuring health care quality. Investigation into possible risk factors for complications is a popular topic for research. Studies are often designed to evaluate either patient related factors or surgeon related factors that may lead to an increase in adverse events. Common outcomes reported include surgical time, length of hospital stay, infections, injury to surrounding organs, surgeon volume, readmission, and mortality. However,

[name]

risk factors and outcome measures will vary depending on the patient population and procedures being studied.

Commonly studied patient related factors that may impact perioperative morbidity include age, body mass index (BMI), American Society of Anesthesiologists classification (ASA), and medical comorbidities such as diabetes, heart disease, and pulmonary disease. Visser and colleagues performed a systematic review that analyzed 30 articles [2]. They found 9 significant patient related factors that contribute to surgical outcomes. Age, BMI, and ASA classification were the most commonly reported and most significant factors. Increased rates of surgical site infection have been described in patients with recent hospitalization prior to surgery [3, 4]. Borenstein and colleagues found that prior admission within 30 days was associated with an increased risk of adverse outcomes such as hospital acquired infections, adverse drug reactions and length of stay [5]. However, few studies have assessed prior admissions beyond 30 days.

Patients who meet their insurance deductibles are likely more eager to proceed with an elective procedure, as they will little or no out of pocket cost. Many physician practices notice a surge of patients seeking care at the end of the year compared to other times of the year. Patients who have met their deductible likely utilize more healthcare resources because they have more health problems, or have had more procedures performed during that year. Thus there may be potential for sicker and more complicated patients to undergo surgery at the end of the year as compared to other times of the year. These patients may suffer more surgical complications that could then lead to an overall greater cost for healthcare. If so, this difference could impact future health care policy and rationing of resources.

Surgeon related factors that contribute to perioperative morbidity have also become increasingly important and some authors have evaluated these possible factors. Surgeon related factors that have been studied include surgeon volume, surgeon workload per day, procedure timing, and trainee participation. One study found that low-volume surgeons have a higher risk of complications than high-volume surgeons [6]. Hsu and colleagues found that patients receiving an implantable cardioverter-defibrillator implant in the afternoon/evening and on weekends or holidays had higher rates of adverse events [7]. The total number of hours a surgeon operates per day was found to be independently associated with an increased risk of complications when performing pulmonary lobectomies [8]. Trainee participation has been associated with major complications in vaginal hysterectomy and with minor complications in all routes of hysterectomy [9].

Prior studies have often evaluated the “July effect” which is the beginning of a new academic year at teaching hospitals. This time of the year is important, as it is when trainees are moving up in their roles involving patient care and taking on more responsibility. Not only are new interns involved in patient care but trainees at all levels are in participating in a new role. Recently graduated senior residents are now in attending surgeon positions. Findings have

been conflicting on whether there are differences in outcomes and complications at this time of the year. Englesbe and colleagues found an 18% higher postoperative morbidity rate and 41% high mortality rate in July-August compared to April-June [10]. Likewise, another study found higher morbidity and mortality in July for patients after surgery for spinal metastases [11]. However, Highstead, et al. found no difference in complications in July-August compared to April-May for over 3,000 patients admitted to a level 1 trauma service [12].

Identifying which patients are at a higher risk for perioperative morbidity is important to help prevent surgical complications and lower healthcare costs. Proper patient selection and appropriate timing for elective procedures will positively impact these adverse outcomes.

### **Research Plan**

- **Study Design**
  - Retrospective cohort study using Electronic Privacy Identification Center (EPIC) database
- **Setting for the study**
  - Good Samaritan and Bethesda North Hospitals
- **Participants**
  - *Describe*
    - All patients 18 years and older who underwent a surgical procedure in the main operating rooms at Good Samaritan Hospital and Bethesda North Hospital between January 1, 2015 and December 31, 2016.
    - Approximately 9,000 cases are performed annually at the Good Samaritan Hospital main OR and 15,000 cases are performed annually at the Bethesda North main OR.
  - *Inclusion criteria*
    - All persons aged 18 and older undergoing surgical procedures in the main operating room during the study period
  - *Exclusion criteria*
    - Patients under the age of 18
    - Procedures done outside of the main operating suites (Endoscopy suite, Labor and Delivery)
  - *Sample Size*
    - About 48,000 chart review is expected.
- **Data Collection**
  - Basic demographics and surgical procedure data will be collected.

- Date of surgery, surgery location, and surgeon name will be collected.
- Trainee participation will be recorded – resident or fellow participation in case.
- Patient comorbidities will be collected including but not limited to obesity, tobacco use, ASA classification, DM, HTN, heart disease, pulmonary disease, chronic kidney disease, prior surgical history in past 6 months, preoperative lab data.
- Intraoperative surgical complications and hospital length of stay will be collected.
- Insurance information will be collected
- Postoperative complications including but not limited to reoperation, readmission within 90 days of surgery for any reason, death within 90 days will be collected. Complications inherent to most surgical procedures including excessive blood loss, need for blood transfusion, infection, thromboembolic events, and injury to surrounding organs will be collected.

- **Intervention or experimental aspect of the study**
  - Not applicable as it is a retrospective chart review
- **Statistical Analysis**
  - Descriptive statistics will be calculated for demographics, preoperative, and intraoperative information. Chi-squared tests will be employed for categorical variables and t test or Mann-Whitney U test for continuous variables. Mean (SD) values will be used for data meeting the assumptions for normality; median (IQR) values will be used for data not meeting the assumptions for parametric procedures. Multivariate logistic regression model will be implemented for a prediction model.

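### The question is about elective surgery, but the cohort is every adult main-OR case with no elective restriction or stratum, so the all-case December result does not in general estimate the elective effect.

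*Combined protocol and SAP*

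**What the plan says.** All references are to the combined protocol and SAP.

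- **Title:** "Does procedural timing impact perioperative morbidity in elective surgery".
- **Purpose of Study:** "To evaluate if there are differences in perioperative morbidity for elective surgery based on the time of the year surgery is performed".
- **Primary hypothesis (under Hypothesis or Research Question):** "Perioperative morbidity will be highest toward the end of the calendar year (December) corresponding with insurance deductible year-end". The word elective is not repeated here.
- **Background, deductible rationale:** "Patients who meet their insurance deductibles are likely more eager to proceed with an elective procedure". The Background closes on the same population: "Proper patient selection and appropriate timing for elective procedures will positively impact these adverse outcomes".
- **Research Plan, Inclusion criteria:** "All persons aged 18 and older undergoing surgical procedures in the main operating room during the study period". The exclusions are age under 18 and procedures done outside the main operating suites.
- **Sample Size:** about 48,000 charts.
- **Data Collection:** demographics, unspecified surgical procedure data, and an open-ended comorbidity list that includes ASA class. Urgency or case class is not named.
- **Statistical Analysis:** univariable tests and a multivariable logistic model described as a prediction model. No covariate, stratum, subgroup or interaction is named.

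**The concern.** The population in the question and the population in the cohort differ. If the plan is followed as written, the December comparison averages over elective and non-elective cases, and nothing in it separates the two.

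Three errors become possible:

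1. **Dilution.** If December does nothing to non-elective morbidity, a real elective effect is pulled toward the null.
2. **Misattribution.** If December raises non-elective morbidity, the all-case test may reject with no elective effect, and the result could be credited to elective timing. The Background raises factors of this kind itself. It cites surgeon workload per day, and a defibrillator-implant study in which patients treated "in the afternoon/evening and on weekends or holidays had higher rates of adverse events".
3. **Case mix.** The Background expects a surge of patients at year-end, driven by elective demand. If the elective share changes in December and the two groups differ in baseline risk, the crude contrast moves even when neither group has a December effect.

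The Background says a December difference could affect health policy and resource rationing, so the cohort should match the claim.

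**Working it through.** **1. The plan's own figure.** Annual main-OR volumes are 9,000 and 15,000, and the study period is two calendar years: (9,000 + 15,000) × 2 = 48,000. This equals the stated chart count, so no non-elective cases were removed from it. There is no power calculation to reproduce.

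**2. Assumed inputs (none is in the documents).** Non-elective share e = 0.20; morbidity outside December 0.20 non-elective and 0.08 elective; elective December risk ratio (RR) 1.15; December against the other 11 months; equal monthly volume, so 4,000 against 44,000 cases; unadjusted pooled z-test, two-sided 5%.

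**3. Formulas.** With RRn the non-elective December RR:

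- Other months: p0 = 0.20 × 0.20 + 0.80 × 0.08 = 0.040 + 0.064 = 0.104.
- Non-elective weight: w = 0.040 / 0.104 = 0.385.
- All-case RR = w × RRn + (1 − w) × 1.15, and p1 = p0 × all-case RR.
- Power ≈ Φ[(p1 − p0 − 1.96 s0) / s1], with s0 the pooled and s1 the unpooled standard error.

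Elective cases only: 0.092 against 0.080, with 3,200 and 35,200 cases. Here s0 = 0.00504 and s1 = 0.00531, so power = Φ[(0.0120 − 0.00987) / 0.00531] = Φ(0.40) = 0.66.

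**4. Elective effect present (RR 1.15); elective-only power 66% in every row.**

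| RRn | p1 | All-case RR | All-case power |
|---|---|---|---|
| 0.95 | 0.1116 | 1.07 | 33% |
| 1.00 | 0.1136 | 1.09 | 48% |
| 1.06 | 0.1160 | 1.12 | 65% |
| 1.10 | 0.1176 | 1.13 | 76% |
| 1.15 | 0.1196 | 1.15 | 86% |

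Over non-elective shares of 10–30% and non-elective morbidity of 8–20%, w runs from 0.10 to 0.52. At RRn = 1.00 the all-case RR runs from 1.07 to 1.135 and power from 36% to 66%, against 60–70% for elective cases alone. All-case and elective-only power break even at RRn of about 1.06–1.07.

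**5. No elective effect, RRn = 1.15.** p1 = 0.20 × 0.23 + 0.80 × 0.08 = 0.110. The all-case RR is 0.110 / 0.104 = 1.06, and the test rejects about 23% of the time.

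**6. Case mix alone, no effect in either group.**

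- Elective volume +20%, non-elective flat: (0.96 × 0.08 + 0.20 × 0.20) / 1.16 = 0.1007, RR 0.97.
- Elective +20%, non-elective +50%: (0.96 × 0.08 + 0.30 × 0.20) / 1.26 = 0.1086, RR 1.04.

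**7. Surge and effect together.** Elective RR 1.15, RRn 1.00, elective volume +20% in December, total held at 48,000: p1 = (0.96 × 0.092 + 0.20 × 0.20) / 1.16 = 0.1106. The all-case RR is 1.06 with power 29%, against 72% for elective cases alone. Under these inputs the year-end surge that the Background describes hides the effect it predicts.

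**8. A milder setting.** With 10% morbidity in both groups, elective RR 1.18 and RRn 1.00, all-case power is 89% at a 10% non-elective share and 81% at 20%. Elective-only power is 92% and 88%. Low power is therefore not the core of the point.

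**The case against.** - **The size is unknown and may be small.** The documents never mention emergency cases; their presence is inferred from the all-case wording. With the other inputs unchanged and RRn = 1.00, a 5% non-elective share gives an all-case RR of 1.13 and power of 68% against 73%. A 2% share gives 1.14 and 72% against 74%. If the December effect and the case mix are the same in both groups, the two ratios coincide. All of this stands. It limits the size of the error, but the documents do not show that either condition holds.
- **The hypotheses do not say elective.** This is true, and the July hypothesis does not depend on elective status; the Background cites a study that found "no difference in complications in July-August compared to April-May for over 3,000 patients admitted to a level 1 trauma service". That is a reason to keep non-elective cases in the dataset. It does not rescue the December hypothesis, which rests on the deductible and, through it, on elective choice.
- **Urgency might be captured or adjusted for.** The procedure data could include case class, and a multivariable model is planned. But no definition or use is stated. An urgency main effect would deal with case mix and still average the December effect over both groups.
- **The misattribution case is thinly supported.** The cited workload and holiday findings say nothing about urgency and give no reason to spare elective cases. That is fair: section 5 of the working shows what is possible, not what is likely.

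**Conclusion.** The concern holds and should be fixed. The mismatch between an elective question and an all-case cohort is plain from the text and from the 48,000 count. The all-case December ratio equals the elective one in general only if non-elective cases are negligible, or if effects and case mix agree across the two groups.

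Neither the direction nor the size of the error can be fixed from the documents. Under the stated assumptions, a true elective ratio of 1.15 appears as 1.07 to 1.13 as the non-elective ratio goes from 0.95 to 1.10, and case mix alone moves a null ratio to 0.97 or 1.04. The case-mix figures are for a crude contrast. Confidence is high in the mismatch, not in any particular bias.

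**What to change.** 1. Define elective (scheduled) status, name the case-class or urgency field that supplies it, and extract it. That such a field is recorded is an assumption.
2. Make elective cases the primary analysis cohort for the December hypothesis. Restate the expected N: 48,000 × 0.9 = 43,200 to 48,000 × 0.7 = 33,600 if 10–30% of cases are non-elective (assumed).
3. Report non-elective cases as a separate stratum. Do not treat them as a clean negative control, since workload and holiday timing could affect them too.
4. Report July by the same strata, with the elective stratum answering the stated purpose.
5. If urgency cannot be retrieved, reword the title, purpose and conclusion to all adult main-OR surgery.

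**Cost.** In the text: a cohort definition, one named field and a new N. In practice a second data pull may be needed, because the document is dated 5-9-19 and data collection was planned through August 2017. If results have already been seen, the restriction should be reported as made afterwards. The primary N falls by the non-elective share, and power need not rise: elective-only power is 60–70% for a ratio of 1.15 at 8% morbidity over the assumed range. The gain is that the estimate answers the stated question.

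### A return to the main OR for a complication is both an outcome of the first operation and a new eligible case, so later events can attach to two rows and two months

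*Combined protocol and SAP*

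**What the plan says.** Under Research Plan, Participants, the inclusion criterion is "All persons aged 18 and older undergoing surgical procedures in the main operating room during the study period", with surgery dated "between January 1, 2015 and December 31, 2016". There are two exclusions: "Patients under the age of 18", and a location rule that removes endoscopy and labor-and-delivery procedures. Neither concerns a second operation on the same patient.

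Data Collection lists the outcomes: "Postoperative complications including but not limited to reoperation, readmission within 90 days of surgery for any reason, death within 90 days will be collected". Surgery in the preceding six months is collected too, but as a comorbidity and not as an eligibility or linkage rule.

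On size, Participants states that "Approximately 9,000 cases are performed annually at the Good Samaritan Hospital main OR and 15,000 cases are performed annually at the Bethesda North main OR", and Sample Size states "About 48,000 chart review is expected".

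Statistical Analysis names chi-squared, t or Mann-Whitney tests and a logistic regression. It makes no provision for several operations on one patient. No section defines an index operation, sets a washout, or ties an outcome to a single operation or month.

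**The concern.** Month of surgery is the exposure, and the primary hypothesis is that December is worst. The Background explains this by sicker patients choosing elective surgery once their deductible is met.

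Take a patient operated on 20 November who returns to the main OR on 3 December for a complication and dies on 20 December. She is a November case with a reoperation and a death. The return also meets the inclusion criterion, so she is a December case with a death inside its own 90 days. The December row exists because of the November complication and reflects no decision to have surgery in December.

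Three things are at stake:
- Overall event rates are inflated, because returned patients carry high risk and their later events appear twice.
- Some of December's complications are carried into the months it is compared with, and some earlier complications are carried into December.
- Rows from the same patient are analysed as independent.

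In addition, the prior-surgery covariate is positive by construction on every such return row, so a complication of the first operation becomes a baseline characteristic of the second.

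**Working it through.** **1. The plan's own figure.** (9,000 + 15,000) cases per year x 2 years = 48,000. This matches the stated size exactly, with nothing removed for repeat operations.

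The documents give no reoperation, morbidity or mortality rate, so every rate below is an assumption. Let r be return operations per first operation, 1-5%.

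**2. How many rows are returns.** Index operations = 48,000/(1 + r).
- r = 1%: 47,525 index operations and 475 returns.
- r = 5%: 45,714 index operations and 2,286 returns.

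**3. Inflation of 90-day deaths.** Assume 1% mortality per index operation and mortality d of 4-8% in returned patients. Ratio of per-row rate to index rate = (0.01 + r x d)/(1 + r)/0.01.
- r = 1%, d = 4%: 0.0104/0.0101 = 1.03.
- r = 3%, d = 8%: 0.0124/0.0103 = 1.20.
- r = 5%, d = 8%: 0.0140/0.0105 = 1.33.

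**4. Inflation of overall morbidity.** Assume 10% index morbidity, with 30-50% of return rows flagged with a complication of their own.
- Low end: (0.10 + 0.01 x 0.3)/1.01 = 10.2%.
- High end: (0.10 + 0.05 x 0.5)/1.05 = 11.9%.

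**5. How many returns cross a month end.** With the index day uniform over a month of L = 30.4 days and a delay t to return of at most 90 days, the share falling in a later month is the mean of min(t, L)/L. For exponential delays with decay constants of 7, 14 and 30 days this gives 23%, 41% and 61%. For a uniform delay it is 1 - 30.4/180 = 83%. Looking backward from the 31 December dates gives 24%, 42%, 61% and 83% of December's returns coming from earlier months.

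These are shares of returns. As a share of all December rows, carried-in returns are r x share/(1 + r):
- Smallest: 0.01 x 0.24/1.01 = 0.2%.
- Largest with exponential delays: 0.05 x 0.61/1.05 = 2.9%.
- Uniform delay: 0.05 x 0.83/1.05 = 4.0%.

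**6. Effect on the December ratio.** Assume 8% morbidity in a typical month, 9.6% in December (true ratio 1.20), 40% in return rows, return rates proportional to risk, half of December's returns falling later, and equal monthly volumes. December then has 0.5 x 1.2r + 0.5 x r = 1.1r returns per index case.

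| r | December rate | Typical month | Ratio | Ratio if no return crossed a month end |
|---|---|---|---|---|
| 1% | (0.096 + 0.0044)/1.011 = 0.0993 | 0.084/1.01 = 0.0832 | 1.194 | (0.1008/1.012)/0.0832 = 1.198 |
| 5% | (0.096 + 0.022)/1.055 = 0.1118 | 0.100/1.05 = 0.0952 | 1.174 | (0.120/1.06)/0.0952 = 1.189 |

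The wrong-month part costs about 0.004 to 0.014 of the ratio. The rest of the dilution comes from adding return rows at all. Against a month that receives December's returns, the ratio reads 1.16-1.19.

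A second set of assumptions also gives 1.17-1.19 for December against the rest: 10% against 12% risk, reoperations at 20-50% of complications, 30-50% of return rows flagged, and 20-60% spilling into the next month.

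With equal risk in every month, each month has the same return fraction and the ratio is exactly 1.00.

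**7. Independence.** Suppose 5% of patients have one return. The sum of squared rows per patient over the sum of rows is (0.95 x 1 + 0.05 x 4)/1.05 = 1.095. Standard errors are too small by a factor of √(1 + 0.095 x ρ), where ρ is the within-patient correlation: about 1.4% at ρ = 0.3 and 4.7% at ρ = 1.

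**The case against.** The strongest reply has four parts.

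*The text speaks of patients and persons, and 48,000 is a rounded planning figure.* This stands in part: the unit of analysis is never stated, and an unwritten one-row-per-patient extraction would avoid the extra rows. But the figure equals total case volume with nothing removed, which favours a per-case reading. Even one row per patient would need a rule saying which operation, and so which month, represents the patient.

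*The title and purpose concern elective surgery, and unplanned returns are generally not elective.* Applying that scope would remove many of these rows. The eligibility criteria do not apply it, so the protection is not in the plan.

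*The effect on the December contrast is small.* This stands. A reader might infer from the 24-83% figures that much of December's caseload is carried over, or that a December excess could be an artefact. The documents support neither. Those figures are shares of returns, and under the assumptions above carried-in rows are at most about 4% of December's cases. With equal monthly volumes the mechanism yields no difference where none exists. A busier year end, as the Background anticipates, would give December proportionally fewer carried-in returns and so would not raise its rate.

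*A blanket 90-day washout is a poor remedy.* This also stands. The Background names patients with several procedures in the year as part of the mechanism, so a washout would remove some of the group under study. It would also turn staged or unrelated operations into complications. Operations on days 0, 80 and 160 leave the third unplaced: it is too close to the second to be an index case and too late to be an outcome of the first. Filtering early 2015 would need late-2014 dates, which Data Collection does not say the prior-surgery item records.

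**Conclusion.** The point holds as a gap in the definition of a case that should be closed before analysis. Following the criteria as written, a complication return enters as a new row dated to its own month, and 90-day events shared by two operations attach to both.

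At assumed return rates of 1-5%, 90-day deaths are inflated by about 3-33% (the top figure needs the upper end of both assumed ranges), and a true December ratio of 1.20 reads about 1.17-1.19. The error in standard errors from these returns alone is small.

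A reader might also infer that every complication is counted twice. It is not: the reoperation itself is counted once, as an outcome of the first operation. The duplication lies in the extra row and in later events inside both 90-day windows. Only returns that cross a month end are misassigned, and returns handled outside the main OR do not re-enter. The bias weakens a real December effect and would not by itself create one.

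**What to change.** Add to Participants and Statistical Analysis:

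- The unit of analysis is an index operation.
- An unplanned or complication-related return to the main OR within 90 days of an earlier main-OR operation counts only as an outcome of that operation, in that operation's month, and does not start a new case. State how a return that follows another return is placed.
- Each 90-day readmission or death is attributed to one index operation, with a stated rule for which one when two precede it.
- Planned, staged or unrelated operations remain index cases, with patient-clustered standard errors or GEE.
- A sensitivity analysis applies a 90-day washout for any main-OR operation.
- For January-March 2015, the rule is applied only where the prior-surgery item gives dates; otherwise the result is checked without those months.

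Surgery dates are already collected, and linking operations within patient is already needed for the 90-day outcomes. The cost is some work to classify returns as related or planned, and slightly fewer cases than 48,000: about 475 to 2,286 fewer at 1-5% returns.

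### Counting 90-day readmission from any cause as a complication lets planned returns into the morbidity count; report unplanned returns alongside it.

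*Combined protocol and SAP*

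**What the plan says.** Under postoperative complications, the Data Collection part of the Research Plan reads: "reoperation, readmission within 90 days of surgery for any reason, death within 90 days will be collected". Readmission is therefore explicitly all-cause over 90 days. Reoperation carries no statement of planned or unplanned. No section separates planned from unplanned returns or excludes staged procedures.

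The primary hypothesis is: "Perioperative morbidity will be highest toward the end of the calendar year (December) corresponding with insurance deductible year-end". The Background gives the reasoning: "Patients who meet their insurance deductibles are likely more eager to proceed with an elective procedure", and "Thus there may be potential for sicker and more complicated patients to undergo surgery at the end of the year".

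The Statistical Analysis section names chi-squared tests for categorical variables and adds "Multivariate logistic regression model will be implemented for a prediction model". It does not say which items make up perioperative morbidity or which months are compared with December. The Data Collection list also states "Insurance information will be collected".

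**The concern.** A planned second-stage procedure or a scheduled admission is not a surgical complication, yet the readmission item counts it as one. Two consequences are possible if the item enters the December measure.

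- **Dilution.** If planned returns are equally common after surgery in every month, they add the same number of non-complication events per hundred cases everywhere. The risk ratio moves toward 1 and the variance rises. This needs no assumption about insurance.
- **Bias.** The study supposes that deductible status drives demand for elective care, and a planned return is elective care. Most of the 90 days after a December operation fall in the next deductible year. Planned returns could therefore differ after December surgery for scheduling reasons alone. The protocol does not say this of planned returns; it is an inference. A reset could lower them, and sicker year-end patients could raise them.

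Adjusting for comorbidity does not separate the two kinds of return.

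**Working it through.** **1. The plan's own figure.** The Research Plan states: "Approximately 9,000 cases are performed annually at the Good Samaritan Hospital main OR and 15,000 cases are performed annually at the Bethesda North main OR". Over two years, (9,000 + 15,000) × 2 = 48,000, which matches the expected number of charts. This is a case count. The documents give no event rate, alpha or power, so every rate below is an assumption.

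**2. Dilution.** Inputs:
- December n = 48,000 / 12 = 4,000 and other months 44,000 (equal months assumed).
- Two-sided alpha 0.05 (assumed).
- True risk ratio 1.18, borrowed from the July-August study cited in the Background, because no December effect is given.
- Unplanned rate u, and planned rate q equal in all months, with no overlap between the two.

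Formulas: p(other) = u + q; p(Dec) = 1.18u + q; observed RR = p(Dec) / p(other). Power = Φ[(|p(Dec) − p(other)| − 1.96·SE0) / SE1], with SE0 the pooled and SE1 the unpooled standard error.

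| q | u = 5%: observed RR | power | u = 10%: observed RR | power |
|---|---|---|---|---|
| 0 | 1.18 | 0.69 | 1.18 | 0.94 |
| 1% | 6.9/6.0 = 1.15 | 0.62 | 12.8/11.0 = 1.16 | 0.92 |
| 2% | 7.9/7.0 = 1.13 | 0.56 | 13.8/12.0 = 1.15 | 0.90 |
| 3% | 8.9/8.0 = 1.11 | 0.52 | 14.8/13.0 = 1.14 | 0.89 |
| 5% | 10.9/10.0 = 1.09 | 0.44 | 16.8/15.0 = 1.12 | 0.85 |

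The absolute difference stays at 0.9 points (u = 5%) or 1.8 points (u = 10%). What is lost is the ratio and the precision.

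**3. Possible bias.** I enumerated all 731 surgery dates from 1 January 2015 to 31 December 2016 (62 in December). For each I took the share of the follow-up days that fall in the post-reset period. Net exposure is the December mean minus the mean for other months.

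| Post-reset period | Days 1-90: Dec, other, net | Days 1-30: Dec, other, net |
|---|---|---|
| From the next 1 January only | 0.833, 0.059, 0.775 | 0.500, 0, 0.500 |
| Any January-March day, all patients | 0.833, 0.193, 0.640 | 0.500, 0.224, 0.276 |
| Any January-June day, all patients | 0.833, 0.465, 0.368 | 0.500, 0.496, 0.004 |

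Shift in the December rate = q × (post-reset ratio − 1) × net. I assume q of 2% to 4% and a ratio of 0.5 to 1.25.
- Net 0.775: 4% × (−0.5) × 0.775 = −1.55 points, to 4% × 0.25 × 0.775 = +0.77 points.
- Net 0.500: −1.00 to +0.50 points.
- Net 0.368: −0.74 to +0.37 points.
- Net 0.004: about zero.
- Net 0.775 with only half of planned returns sensitive to the deductible: −0.77 to +0.39 points.

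**4. Scale.** Allocating cases by date, December n = 48,000 × 62/731 = 4,071, with 43,929 in other months. The 95% half-width, 1.96 × √[p(1 − p)(1/4,071 + 1/43,929)], is 0.70, 0.96 and 1.15 points at p = 5%, 10% and 15%. I tried six scenarios per model: q = 2% or 4%, with ratio 0.5, 0.75 or 1.25. Against 0.96 points, one of six exceeds it at net 0.775 and one of six at net 0.500. None does at net 0.368 or if half of returns are sensitive.

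**The case against.** **It is a collection list, not an endpoint.** These items are to be collected, and collecting all-cause events rules out no later split. The larger gap is that morbidity and the December comparator are undefined. This stands, and it makes the point conditional. But any definition that uses readmission must settle planned status, and the only rule written down is all-cause.

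**Reoperation under a complications heading ordinarily means reoperation for a complication.** This stands. A reader might infer that the plan counts staged operations as reoperations; the text does not establish that. Only the readmission wording is explicit.

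**All-cause readmission is objective and needs no retrospective judgement of intent.** This stands. A reader might infer that it should be replaced, but doing so would exchange a known dilution for possible misclassification. It should stay.

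**The deductible mechanism is not in the documents, and its size is assumed throughout.** This stands too. A reader might take 83% against 6% of follow-up days as showing that December is biased. That contrast is the most favourable model: it treats a February return after January surgery as outside the reset. Other reasonable models bring the net exposure down as far as 0.004, and no figure in the documents chooses among them. The dilution does not depend on this argument.

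**Conclusion.** The point holds as a cheap improvement and should not be put higher. If all-cause readmission enters the December measure, planned admissions count as morbidity. The table's power loss from dilution ranges from slight (0.94 to 0.92) to substantial (0.69 to 0.44), depending on assumed unplanned rates of 5% or 10%, assumed planned rates of 1% to 5%, and a borrowed risk ratio of 1.18.

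Bias tied to the deductible year is possible in either direction, but it is neither shown nor excluded. A conclusion that the December result will be biased would go beyond the documents.

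Death, intraoperative complications, length of stay, blood loss, transfusion, infection, thromboembolism and organ injury are not affected.

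**What to change.** - Keep all-cause 90-day readmission as collected.
- Report beside it unplanned readmission and unplanned return to the operating room, both within 90 days.
- Fix the rule for planned status in advance. Use admission type or case class if the database holds it (assumed); otherwise review the returns only. Apply the rule without knowledge of surgery month, because classification that varied by month would itself create a bias.
- Tabulate planned returns by month and by insurance type, to show whether a deductible-related pattern exists.
- State whether reoperation means reoperation for a complication.

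**Cost.** With the field available: a sentence of definition, one data item and one table. Without it, at an assumed return rate of 5% to 15%, 48,000 × 0.05 = 2,400 to 48,000 × 0.15 = 7,200 returns need classifying, of which about 200 to 600 follow December surgery. The document is dated May 2019 and its timetable ends data collection in August 2017, so adding a field may mean returning to the database. The unplanned outcomes will have fewer events and some misclassification. The sample of 48,000 does not change.
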